14.2 New York Heart Association Classification of Cardiac Disease

Class	Functional Capacity	Objective Assessment
I	Patients with cardiac disease but without resulting limitations of physical activity. Ordinary physical activity does not cause undue fatigue, palpitation, dyspnea, or anginal pain.	No objective evidence of cardiovascular disease.
II	Patients with cardiac disease resulting in slight limitation of physical activity. They are comfortable at rest. Ordinary physical activity results in fatigue, palpitation, dyspnea, or anginal pain.	Objective evidence of minimal cardiovascular disease.
III	Patients with cardiac disease resulting in marked limitation of physical activity. They are comfortable at rest. Less than ordinary activity causes fatigue, palpitation, dyspnea, or anginal pain.	Objective evidence of moderately severe cardiovascular disease.
IV	Patients with cardiac disease resulting in inability to carry on any physical activity without discomfort. Symptoms of heart failure or the anginal syndrome may be present even at rest. If any physical activity is undertaken, discomfort is increased.	Objective evidence of severe cardiovascular disease.

Source: The Criteria Committee of New York Heart Association. Nomenclature and Criteria for Diagnosis of Diseases of the Heart and Great Vessels. 9th Ed. Boston, MA: Little, Brown & Co; 1994:253-256. ⁽¹⁶⁾

14.3 Cockcroft-Gault Equation

$$\text{Creatinine Clearance} = \frac{0.85 (140 - \text{age [years]}) \times \text{weight [kg]}}{72 \times (\text{serum creatinine [mg/dL]})}$$

OR

$$\frac{0.85 (140 - \text{age [years]}) \times \text{weight [kg]}}{0.81 \times (\text{serum creatinine [\mu mol/L]})}$$

Source: Cockcroft DW, Gault MH. Prediction of creatinine clearance from serum creatinine. *Nephron* 1976;16(1):31-41. ⁽¹⁷⁾

14.4 List of Relevant Cytochrome P₄₅₀ Inhibitors and Inducers

Moderate CYP1A2 Inhibitors		
cimetidine	methoxsalen	
Strong CYP1A2 Inhibitors		
fluvoxamine	ciprofloxacin	
Clinically Significant Enzyme Inducers		
carbamazepine	rifabutin	St. John's wort
phenobarbital	rifampin	phenytoin
rifapentine		

Source: fda.gov/Drugs/DevelopmentApprovalProcess/DevelopmentResources/DrugInteractionsLabeling/ucm093664.htm.

Note that these lists are not exhaustive.

14.5 Exclusionary QT-Prolonging Drugs

The following table contains a list of QT-prolonging drugs according to the Arizona Center for Education and Research on Therapeutics. QT-prolonging drugs with a risk of causing torsades de pointes (TdP) are exclusionary in this study. Patients on a stable dose of drugs with a conditional or possible risk of QT prolongation or drugs that are to be avoided by patients with congenital long QT syndrome may be considered pending discussion and agreement with the project clinician.

Exclusionary QT-Prolonging Drugs

Drug Class	Risk of TdP ^a Name (Brand Name)	Conditional or Possible Risk of TdP ^b Name (Brand Name)	Congenital QTc Name (Brand Name)
Antiangular		ranolazine (Ranexa)	
Antiarrhythmic	amiodarone (Cordarone, Pacerone) bepridil (Vascor) disopyramide (Norpace) dofetilide (Tikosyn) flecainide (Tambocor) ibutilide (Convert) procainamide (Pronestyl, Procan) quinidine (Cardioquin, Quinaglute) sotalol (Betapace)	dronedarone (Multaq)	
Antibiotic	azithromycin (Zithromax) clarithromycin (Biaxin) erythromycin (Erythrocin, EES) moxifloxacin (Avelox) pentamidine (NebuPent, Pentam) sparfloxacin (Zagam)	ciprofloxacin (Cipro) gatifloxacin (Tequin) gemifloxacin (Factive) levofloxacin (Levaquin) ofloxacin (Floxin) roxithromycin (Rulide) telithromycin (Ketek) trimethoprim-sulfa (Sulfa, Bactrim)	
Anticancer	arsenic trioxide (Trisenox) vandetanib (Caprelsa)	Eribulin (Halaven) lapatinib (Tykerb, Tyverb) nilotinib (Tasigna) sunitinib (Sutent)	
Anticonvulsant/ Seizure		felbamate (Felbatrol) fosphenytoin (Cerebyx)	
Antidepressant	citalopram (Celexa)	amitriptyline (Elavil) clomipramine (Anafranil) desipramine (Pertofrane) doxepin (Sinequan) escitalopram (Lexapro, Cipralex) fluoxetine (Prozac, Sarafem) imipramine (Norfranil)	

Exclusionary QT-Prolonging Drugs

Drug Class	Risk of TdP ^a Name (Brand Name)	Conditional or Possible Risk of TdP ^b Name (Brand Name)	Congenital QTc Name (Brand Name)
Antiemetic	domperidone (Motilium) droperidol (Inapsine)	lithium (Eskalith, Lithobid) nortriptyline (Pamelor) paroxetine (Paxil) protriptyline (Vivactil) sertraline (Zoloft) trazodone (Desyrel) trimipramine (Surmontil) venlafaxine (Effexor)	dolasetron (Anzemet) granisetron (Kytril) ondansetron (Zofran) tamoxifene (Nolvadex)
Antifungal		fluconazole (Diflucan) itraconazole (Sporanox) ketoconazole (Nizoral) voriconazole (Vfend)	
Antihistamine	astemizole (Hismanal) terfenadine (Seldane)	diphenhydramine (Benadryl, Nytol)	
Antihypertensive/ Diuretic		indapamide (Lozol) isradipine (Dynacirc) moexipril/HCTZ (Uniretic) nicardipine (Cardene)	
Antilipemic/ Hypercholesterolemia	probucol (Lorelco)		
Antimalarial	chloroquine (Aralen) halofantrine (Halfan)		
Antipsychotic	chlorpromazine (Thorazine) haloperidol (Haldol) mesoridazine (Serentil) pimozide (Orap) thioridazine (Mellaril)	amisulpride (Solian) clozapine (Clozaril) iloperidone (Fanapt) paliperidone (Invega) quetiapine (Seroquel)	

Exclusionary QT-Prolonging Drugs

Drug Class	Risk of TdP ^a Name (Brand Name)	Conditional or Possible Risk of TdP ^b Name (Brand Name)	Congenital QTc Name (Brand Name)
Antiviral/ HIV infection		risperidone (Risperdal) sertindole (Serolect, Serlect) ziprasidone (Geodon) foscarnet (Foscavir)	
Appetite suppressant/dieting, weight loss			fenfluramine (Pondimin) phentermine (Adipex, Fastin) sibutramine (Meridia)
Benign prostatic hyperplasia		alfuzosin (Uroxatral)	
β2-receptor/asthma			albuterol (Proventil, Ventolin)
Bladder antispasmodic			Tolterodine (Detrol LA, Detrol)
Bronchodilator			ephedrine (Broncholate, Rynatuss) levalbuterol (Xopenex) metaproterenol (Alupent, Metaprel) terbutaline (Brethine) epinephrine (Bronkaid, Primatene) isoproterenol (Isupres, Medihaler- Iso) dobutamine (Dobutrex)
Catecholamine		galantamine (Reminyl)	
Cholinesterase inhibitor/ Dementia, Alzheimer's			
CNS stimulant/ADHD			amphetamine (Adderall, Dexedrine) dexmethylphenidate (Focalin) lisdexamfetamine (Vyvanse) methlphenidate (Concerta,

Exclusionary QT-Prolonging Drugs

Drug Class	Risk of TdP ^a Name (Brand Name)	Conditional or Possible Risk of TdP ^b Name (Brand Name)	Congenital QTc Name (Brand Name)
Decongestant/allergies, sinusitis, asthma			Ritalin) Phenylpropanolamine (Acutrim, Dexatrim) pseudoephedrine (Pediacare, Sudafed)
Dopaminergic		amantadine (Symmetrel)	
Endocrine		octreotide (Sandostatin)	
Erectile dysfunction		vardenafil (Levitra)	
GI stimulant/Heartburn	cisapride (Propulsid)		
Imaging contrast agent/ Echocardiography		perflutren lipid microspheres (Definity)	
Immunosuppressant		fingolimod (Gilenya) tacrolimus (Prograf)	
Inotropic agent/heart failure, hypotension, shock			dopamine (Intropine)
Local anesthetic			cocaine (Cocaine)
Muscarinic receptor antagonist/ overactive bladder		solifenacin (VESIcare)	
Muscle relaxant		tizanidine (Zanaflex)	
Norepinephrine reuptake inhibitor/ADHD			atomoxetine (Strattera)
Opiate agonist	levomethadyl (Orlaam) methadone (Dolophine, Methadose)		
Oxytocic		oxytocin (Pitocin)	
Peptic ulcer/GERD/ H ₂ -receptor antagonist		famotidine (Pepcid)	

Exclusionary QT-Prolonging Drugs

Drug Class	Risk of TdP ^a Name (Brand Name)	Conditional or Possible Risk of TdP ^b Name (Brand Name)	Congenital QTc Name (Brand Name)
Protease inhibitor/HIV		atazanavir (Reyataz) ritonavir (Norvir)	
Sedative		chloral hydrate (Noctec)	
Sympathomimetic/asthma/ COPD			salmeterol (Serevent)
Uterine relaxant/prevent premature labor			ritodrine (Yutopar)
Vasoconstrictor, inotrope/shock, low blood pressure			norepinephrine (Levophed)
Vasoconstrictor, decongestant/ low blood pressure			phenylephrine (Neo-Synephrine) midodrine (ProAmatine)

Source: Based on Woosley RL. Drugs That Prolong the QT Interval and/or Induce Torsades de Pointes. Arizona Center for Education and Research on Therapeutics. azcert.org/medical-pros/drug-lists/printable-drug-list.cfm. Last revised 24 June 2012.

Abbreviations: ADHD = Attention deficit hyperactivity disorder; COPD = chronic obstructive pulmonary disorder; CNS = central nervous system; EES = erythromycin ethylsuccinate; GERD = gastroesophageal reflux disease; TdP = Torsades de Pointes.

Exclusions applicable only to listed drugs. Names in parenthesis are United States trade names. Drugs often have more than one brand name. For this table, only the 2 most common brand names are included.

a Drugs that are generally accepted by authorities to have a risk of causing TdP.

b Drugs that may prolong the QT interval but at this time lack substantial evidence for causing TdP.

c Drugs to be avoided, if possible, by patients with Congenital Long QT Syndrome.

14.6 Amendment 2 Detailed Summary of Changes

The primary section(s) of the protocol affected by the changes in Amendment 2 are indicated. The corresponding text has been revised throughout the protocol.

Change 1: Remove the exclusion criterion relating to treatment with strong CYP inhibitors or inducers.

The primary change occurs in Section [5.2 Exclusion Criteria](#):

Deleted text: ~~16. Patients requiring treatment with strong CYP3A4 and CYP2C19 inducers and/or inhibitors and moderate inhibitors of CYP2C9. Treatment with strong CYP3A4 and CYP2C19 inducers and/or inhibitors must be discontinued at least 14 days before the first dose of study drug. Treatment with moderate inhibitors of CYP2C9 must be discontinued at least 7 days before the first dose of study drug.~~

Rationale for Change:

This change, which removes enrollment restrictions for patients taking CYP3A4, CYP2C9, or CYP2C19 inhibitors and/or inducers in this study, was made to allow more flexibility in patient enrollment based on updated data on MLN0128 metabolism by specific CYP isoforms.

Change 2: Update the list of concomitant medications prohibited during the study.

The primary change occurs in Section [6.5 Excluded Concomitant Medications and Procedures](#):

Previous text: Strong CYP3A4 and CYP2C19 inducers and/or inhibitors and moderate inhibitors of CYP2C9. After completing the required PK/ECG assessment period (Cycle 1, Day 3), treatment with 1 or more of the strong CYP3A4 or CYP2C19 inhibitors and/or inducers and moderate inhibitors of CYP2C9 may be considered after consultation with the project clinician. A list of strong inhibitors and strong inducers of CYP2C9, CYP2C19, and CYP3A4 is included in Section [14.4](#).

Amended or new wording: ~~Strong cytochrome P450 (CYP) 1A2 inhibitors and CYP CYP3A4 and CYP2C19 inducers and/or inhibitors and moderate inhibitors of CYP2C9.~~
~~After completing the required PK/ECG assessment period (Cycle 1, Day 3), inducers should be administered with caution and at the discretion of the investigator. See treatment with 1 or more of the strong CYP3A4 or CYP2C19 inhibitors and/or inducers and moderate inhibitors of CYP2C9 may be considered after consultation with the project clinician. A list of strong inhibitors and strong inducers of CYP2C9, CYP2C19, and CYP3A4 is included in. Refer to Section 14.4 for a list of these agents. Alternative treatments, if available, should be considered.~~

Rationale for Change:

This change was made to update the recommendations on concomitant medication use during the study based on MLN0128 metabolism by specific CYP isoforms

Change 3: Update the description of potential drug-drug interactions.

The primary change occurs in Section 1.2 Nonclinical Experience

Initial wording: In-vitro, MLN0128 is metabolized by various cytochrome P450 (CYP) enzymes, including 2C19 (35%), 3A4 (28%), and 2C9 (28%); MLN0128 neither inhibited nor induced any of the major CYP enzymes. Additionally, MLN0128 did not inhibit P-glycoprotein (P-gp) but did inhibit breast cancer resistance. At the plasma concentrations expected with the 40 mg dose of MLN0128, there exists a risk for a drug-drug interaction (DDI) with substrates of breast cancer-resistant protein (BCRP) (eg, methotrexate, irinotecan, rosuvastatin, topotecan, lapatinib, imatinib, etc.). Such agents should be avoided from co-administration with MLN0128. Since MLN0128 is metabolized by various CYP enzymes, the risk for clinically significant DDI (2-fold or greater) is considered low; however, given that the 40 mg dose of MLN0128 is the single agent MTD in the every week (QW) dosing schedule, potent inhibitors of CYP3A4 and CYP2C19 enzymes and strong inducers of CYP enzymes should not be administered concomitantly with MLN0128.

Amended or new wording: ~~Recently completed in-vitro-metabolism experiments in human hepatocytes using ¹⁴C-labeled MLN0128 suggest that, MLN0128 is metabolized by various primarily via CYP1A2 (approximately 31% to 40%), with a minor contribution from CYP3A4 (approximately 11% to 22%). These data suggest that MLN0128 is also metabolized by direct glucuronidation (approximately 22%) and an unidentified non-uridine diphosphate glucuronosyltransferase pathway (approximately 18%). The new data differ from the previous in vitro CYP phenotyping data obtained using recombinant CYP enzymes, which suggested the involvement of CYP2C9 (approximately 35%), CYP2C19 (approximately 28%), and CYP3A4 (approximately 28%) in MLN0128 metabolism. cytochrome P450 (CYP) enzymes, including 2C19 (35%), 3A4 (28%), and 2C9 (28%); MLN0128 neither~~

~~inhibited nor induced any of the major CYP enzymes. Additionally, MLN0128 did not inhibit P-glycoprotein (P-gp) but did inhibit breast cancer resistance. At the plasma concentrations expected with the 40 mg dose of MLN0128, there exists a risk for a drug-drug interaction (DDI) with substrates of breast cancer-resistant protein (BCRP) (eg, methotrexate, irinotecan, rosuvastatin, topotecan, lapatinib, imatinib, etc.). Such agents should be avoided from co-administration with MLN0128.~~

~~Since MLN0128 is metabolized by various CYP enzymes, the risk for clinically significant DDI (2-fold or greater) is considered low; however, given that the 40 mg dose of MLN0128 is the single agent MTD in the every week (QW) dosing schedule, potent inhibitors of CYP3A4 and CYP2C19 enzymes and strong inducers of CYP enzymes should not be administered concomitantly with MLN0128. In addition, physiologically based PK modeling and simulation using the new metabolism data for MLN0128 suggest that the risk for a metabolism-based drug-drug interaction with MLN0128 appears to be low. Therefore, strong CYP1A2 inhibitors and CYP inducers (see Section 0) should only be administered with caution and at the discretion of the investigator during the study. Alternative treatments, if available, should be considered.~~

Rationale for Change:

This paragraph was amended to describe updated data on MLN0128 metabolism by specific CYP isoforms.

Change 4: Update the list of relevant CYP inhibitors and inducers.

The primary change occurs in Section 14.4 List of Relevant Cytochrome P450 Inhibitors and Inducers:

Description of the change:	The list of relevant CYP inhibitors and inducers was updated to remove sections listing strong CYP2C19 inhibitors and strong CYP3A4 inhibitors; to add section listing strong and moderate CYP1A2 inhibitors; and update the section listing clinically significant enzyme inducers.
----------------------------	--

Rationale for Change:

This change was made for consistency with updated data on MLN0128 metabolism by specific CYP isoforms.

Change 5: Remove the dietary restrictions related to CYP inhibitors and inducers.

The primary change occurs in Section 6.7 Precautions and Restrictions:

Deleted text:	Dietary restrictions include periods of fasting as described in Section 7.4.16, and in-home daily fasting glucose monitoring (refer to Section 7.4.18). not consuming food or beverages containing the fruit or juices listed in Section
---------------	---

~~14.4 within 1 week before first dose of study drug and throughout the study.~~

Rationale for Change:

This change was made for consistency with new data that removes the necessity for restrictions concerning CYP2C9 and 2C19.

Section [14.4 List of Relevant Cytochrome P450 Inhibitors and Inducers](#) also contains this change.

Change 6: Insert language to reduce the required frequency of radiographic disease assessments for patients who have received at least 1 year of continuous MLN0128 treatment per protocol.

The primary change occurs in footnote “f” in the [Schedule of Events](#):

Added text: **For long term patients, defined as study participation (greater than or equal to) 1 year, a CT (with contrast)/MRI of chest, abdomen, and pelvis will be obtained at intervals of up to every 4 cycles (plus or minus 7 days) as clinically indicated.**

Rationale for Change:

The change was made to reduce the burden and to minimize radiation exposure for long-term patients.

ELECTRONIC SIGNATURES

Signed by	Meaning of Signature	Server Date (dd-MMM-yyyy HH:mm 'UTC')
PPD	Clinical Approval	04-Dec-2017 19:14 UTC

**MLN0128**  
**Statistical Analysis Plan, Study C31002**

**List of Abbreviations and Definitions of Terms**

Abbreviation	Term
AE(s)	adverse event (or events)
ALP	alkaline phosphatase
ALT	alanine aminotransferase
AST	aspartate aminotransferase
ATCC	Anatomical Therapeutic Chemical Classification
ATP	adenosine triphosphate
AUC inf	area under the plasma concentration versus time curve from zero to infinity
AUC t	area under the plasma concentration versus time curve from zero to the last measurable concentration
BMI	body mass index
BUN	blood urea nitrogen
CI	confidence interval
C max	maximum (peak) plasma concentration
CO 2	carbon dioxide
CRF	case report form
DLT	dose limiting toxicity
ECG	electrocardiogram
ECOG	Eastern Cooperative Oncology Group
eCRF	electronic case report form
FDA	Food and Drug Administration
GGT	gamma glutamyl transferase
ICF	informed consent form
IV	intravenous
LDH	lactate dehydrogenase
MedDRA	Medical Dictionary for Regulatory Activities
MTD	maximum tolerated dose
NCI CTCAE	National Cancer Institute Common Terminology Criteria for Adverse Events
PK	pharmacokinetic
QT	measure of the time between the start of the Q wave and the end of the T wave in the electrical cycle of the heart; electrical depolarization and repolarization of the left and right ventricles of the heart
QT c	rate-corrected QT interval (millisec)
QT cB	rate-corrected QT interval (millisec) with Bazett correction
QT cF	rate-corrected QT interval (millisec) Fridericia correction
QT cI	individual baseline corrected rate-corrected QT interval (millisec)
QW	every week; once weekly
SAE	serious adverse event
SAP	statistical analysis plan
SD	standard deviation
t 1/2	terminal disposition half-life

**MLN0128**  
**Statistical Analysis Plan, Study C31002**

Abbreviation	Term
TEAE	treatment emergent adverse event
T max	first time to maximum plasma concentration
ULN	upper limit of the normal range
US	United States
WHO	World Health Organization

## **1. INTRODUCTION**

In general, the purpose of the statistical analysis plan (SAP) is to provide a framework that addresses the protocol objectives in a statistically rigorous fashion, with minimized bias or analytical deficiencies. Specifically, this plan has the following purpose:

To prospectively (a priori) outline the types of analyses and data presentations that will address the study objectives outlined in the protocol, and to explain in detail how the data will be handled and analyzed, adhering to commonly accepted standards and practices of biostatistical analysis in the pharmaceutical industry.

This SAP only covers the analyses to be performed for the clinical data collected at the sites in the eCRF. The ECG QTc analyses from the Holter monitor will be in a separate SAP prepared by CardioCore. The QTc-PK analyses will be in a SAP prepared by Metrum Research Group.

### **1.1 Study Design**

This is an open label, single-arm, multicenter study to evaluate the effect of a single dose of 40 mg MLN0128 on the electrocardiographic QT/QTc interval in patients with advanced solid tumors. The study will collect time-matched PK and ECG data before and after MLN0128 administration at the time points specified in the Schedule of Events in the protocol.

Patients may continue to receive MLN0128 if, in the opinion of the investigator, the patients are deriving clinical benefit. Treatment may continue until disease progression, unacceptable MLN0128-related toxicity, withdrawal of consent, or for up to 12 months (whichever occurs first).

Approximately, 30 patients will be enrolled from approximately 6 study centers in the US.

### **1.2 Study Objectives**

Primary objective:

- To characterize the effect of a single dose of 40 mg MLN0128 on the electrocardiographic QT/QTc interval in patients with advanced solid tumors.

Secondary objective:

- To evaluate the safety, tolerability, and pharmacokinetics of MLN0128 in patients with advanced solid tumors.

## **2. POPULATIONS FOR ANALYSIS**

### **2.1 Safety Population**

All patients who receive at least 1 dose of MLN0128 will be included in the safety population. This population will be used for safety analyses.

### **2.2 PK Population**

All patients who receive at least 1 dose of MLN0128 and have sufficient concentration-time data to calculate one or more PK parameters will be included in the PK population. All PK analyses will be performed using the PK population.

## **3. HYPOTHESES AND DECISION RULES**

Not applicable.

## **4. INTERIM ANALYSIS**

Not applicable.

## **5. STATISTICAL METHODOLOGY**

Statistical analyses will be primarily descriptive and graphical in nature.

In general, the number of observations, mean, standard deviation (SD), median, minimum, and maximum will be displayed for continuous variables, and the number and percent for categorical data, unless specified otherwise. For PK related parameters, the geometric mean and coefficient of variation will also be presented.

## **5.1 Sample Size Justification**

Based on historical data, the within-subject standard deviation in QTcF change from baseline is approximately 9 msec. A sample size of 30 evaluable patients will be needed to detect a half-width of 2.7 msec of a 2-sided 90% CI for the mean change from baseline in QTcF.

## **5.2 Randomization and Stratification**

Not applicable.

## **5.3 Unblinding**

Not applicable.

## **5.4 Data Handling**

### **5.4.1 Methods for Handling Missing Data**

All available data will be included in data listings and tabulations. Data that are potentially spurious or erroneous will be examined under the auspices of standard data management operating procedures.

#### **5.4.1.1 Missing/Partial Dates in Adverse Events/Concomitant Therapies**

Missing and incomplete start dates will be imputed based on the algorithm described below.

The algorithm will be used only if the end date indicates that the adverse event was not resolved or the therapy was not ended before the first administration of study drug.

Adverse events or concomitant therapies with start dates that are completely or partially missing will be analyzed as follows:

If the start date has month and year but day is missing, the adverse event will be considered treatment-emergent or the therapy concomitant if both the month and year of the start date are on or after the month and year of the date of the first dose of MLN0128 and on or before the month and year of the date of the last dose of MLN0128 plus 30 days.

If the start date has year, but day and month are missing, the adverse event will be considered treatment -emergent or the therapy concomitant if the year of the start date is on or after the year of the date of the first dose of MLN0128 and on or before the year of the date of the last dose of MLN0128 plus 30 days.

If the start date of an adverse event or therapy is completely missing, then the event is assumed to be treatment-emergent or the therapy concomitant.

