8.1.9 Safety Analysis

Safety will be evaluated by the incidence of AEs, severity and type of AEs, and by changes from baseline in the patient's vital signs, weight, and clinical laboratory results using the safety population. Exposure to study drug and reasons for discontinuation will be tabulated.

TEAEs that occur after administration of the first dose of study drug and through 30 days after the last dose of study drug will be tabulated.

AEs will be tabulated according to the Medical Dictionary for Regulatory Activities (MedDRA) and will include the following categories:

- TEAEs
- Drug-related TEAEs
- Grade 3 or higher TEAEs
- Grade 3 or higher drug-related TEAEs
- The most commonly reported TEAEs
- SAEs

A listing of TEAEs resulting in study drug discontinuation will be provided.

Descriptive statistics for the actual values of clinical laboratory parameters (and/or change from baseline in clinical laboratory parameters) will be presented for all scheduled measurements over time. Mean laboratory values over time will be plotted for key laboratory parameters.

Descriptive statistics for the actual values (and/or the changes from baseline) of vital signs and weight over time will be tabulated by scheduled time point.

Shift tables for laboratory parameters will be generated based on changes in NCI CTCAE grade from baseline to the worst postbaseline value. Graphical displays of key safety parameters, such as scatter plots of baseline versus worst postbaseline values, may be used to understand the MLN0128 safety profile.

All concomitant medications collected from screening through the study period will be classified to preferred terms according to the World Health Organization (WHO) drug dictionary.

Additional safety analyses may be performed to most clearly enumerate rates of toxicities and to further define the safety profile of MLN0128.

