## **5.7 Treatments and Medications**

### **5.7.1 Concomitant Medications**

Concomitant medications will be coded using the March 2014 version of the World Health Organization (WHO) Drug Dictionary Enhanced. The number and percentage of patients taking concomitant medications from the date of the first dose of study drug will be tabulated by generic term.

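### SAP 5.4.1.1 applies an adverse-event onset test to therapies, so the concomitant-medication table may omit ongoing therapies whose partial start date falls before the first-dose month or year

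*SAP*

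**What the plan says.** SAP 5.4.1.1 handles incomplete start dates for adverse events and therapies together. It first limits the algorithm to items whose end date shows that the event had not resolved or "the therapy was not ended before the first administration of study drug". Three cases follow:

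- **Day missing.** The rule makes "the therapy concomitant if both the month and year of the start date are on or after the month and year" of the first dose. There is also an upper limit at the month and year of last dose plus 30 days.
- **Day and month missing.** The rule makes "the therapy concomitant if the year of the start date is on or after the year of the date of the first dose of MLN0128", with the matching upper limit by year.
- **Nothing known.** "If the start date of an adverse event or therapy is completely missing, then the event is assumed to be treatment-emergent or the therapy concomitant".

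The section does not say what happens to a therapy whose partial start date falls before the first-dose month or year.

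The table these flags feed is described in SAP 5.7.1: the number and percentage of patients "taking concomitant medications from the date of the first dose of study drug will be tabulated by generic term". SAP 5.4.1 says that all available data go into both listings and tabulations. Protocol 8.1.9 says "All concomitant medications collected from screening through the study period will be classified to preferred terms", and SAP section 6 declares no departure from the protocol.

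**The concern.** Onset on or after first dose is what makes an adverse event treatment-emergent, and SAP 5.10.1.1 defines it that way. A therapy is concomitant for a different reason: its use overlaps treatment, whenever it began. Applying the onset test to therapies turns a question about use into one about initiation.

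What is at stake is the completeness of the background-medication table. This is a single-arm QT study without placebo or positive control (Protocol 1.4), so readers will look to that table to see what else patients were taking. Protocol 5.2 (criterion 12) and 6.5 allow patients on a stable dose of drugs with conditional or possible QT risk to be considered. Protocol 6.5 also leaves strong CYP1A2 inhibitors and CYP inducers to the investigator's discretion, with caution. A drug already at a stable dose at entry began before first dose. If its start date is only partly recorded, it can fall on the wrong side of this rule, and the error runs only towards undercounting.

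**Working it through.** The plan states no figure on this point, so the check is one of logic.

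**Step 1: what reaches the test.** By the limiting sentence in SAP 5.4.1.1, every therapy tested had not ended before first dose. It was either in use at first dose or started later.

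**Step 2: what an early failure means.** A partially dated therapy fails the lower limit only if its known start month or year precedes that of first dose. Combined with step 1, it started before first dose and had not ended by then. It is therefore in use at first dose.

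**Step 3: apply the rule.** The illustrative dates, which are not from the documents, are first dose in March 2015 and last dose plus 30 days in September 2015. Every therapy below is ongoing.

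| Recorded start | Comparison made by SAP 5.4.1.1 | Result as written | Use overlaps treatment? |
|---|---|---|---|
| Feb 2015 | Feb 2015 is before Mar 2015 | condition not met | yes |
| Jun 2010 | Jun 2010 is before Mar 2015 | condition not met | yes |
| 2014 | 2014 is before 2015 | condition not met | yes |
| 2010 | 2010 is before 2015 | condition not met | yes |
| Mar 2015 | within Mar to Sep 2015 | concomitant | yes |
| 2015 | same year | concomitant | yes |
| wholly missing | assumed | concomitant | yes |

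The rule classes 3 of 7 as concomitant; an overlap criterion classes 7 of 7. These counts show how the rule behaves on chosen cases. They do not estimate a rate.

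**Step 4: compare the same drug under three recordings.** Take a drug begun in June 2010 and still taken.

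- Start date complete: 5.4.1.1 is not engaged, and the use criterion of 5.7.1 counts it.
- Day missing: the condition in 5.4.1.1 is not met.
- Start date wholly missing: 5.4.1.1 assumes it concomitant.

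The middle case carries more information than the last, and that information makes it certain that the drug began before first dose. It is nonetheless the only one of the three that is not classed as concomitant.

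**The case against.** The strongest reply is textual. SAP 5.4.1.1 says a therapy is concomitant *if* the partial date falls in the window. It does not say *only if*, and it has no clause sending the rest to non-concomitant. One could hold that 5.4.1.1 settles uncertain starts while 5.7.1, which speaks of use, governs the table; on that view the plan is merely unclear about precedence. It is true that the exclusion is inferred. But the SAP gives no other disposition for these records, and a programmer coding the section as it stands would leave them out. If the sponsor means otherwise, the text has to say so, because the literal rule conflicts with 5.4.1 and 5.7.1.

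Other objections limit the point, and they stand:

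- A reader might infer that long-term medications in general disappear from the table. They do not. Fully dated and wholly undated ongoing therapies are counted, as are partial dates in the first-dose month and year-only dates in the first-dose year. The table counts patients by generic term, so a patient with another qualifying record of the same drug also stays in.
- A reader might want to put a percentage on the loss. The documents give no basis for one. They do not show how often start dates are partial, and they vary on capture: the Schedule of Events records medications from first dose, while Protocol 7.4.3 and 8.1.9 refer to screening.
- A reader might infer that the QTc result is affected. The documents do not support this. The primary endpoint is a within-patient change from a time-matched Day -1 baseline (Protocol 3.1). The Holter QTc and PK/QTc analyses sit in separate plans (SAP 1), and nothing shows the concomitant-medication table feeding them. Protocol 14.5 also requires discussion and agreement with the project clinician for drugs with conditional or possible QT risk, so these are identified outside this table. SAP 5.4.1 keeps all available data in the listings.

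**Conclusion.** The rule is wrong as written for therapies. It admits a therapy because it had not ended before first dose, and then does not class it as concomitant because it started earlier. The affected set is narrow: ongoing therapies whose start date is partial and falls in a month or year before first dose. Within that set every record fails; outside it, no therapy is affected by this fault. The size of the set cannot be derived from the documents.

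The conclusion assumes that a record not meeting the stated condition is treated as not concomitant, which is the operational reading of a section that offers no alternative. The consequence is possible undercounting in a descriptive table, which could include permitted stable-dose drugs with conditional or possible QT risk. No effect on the primary QTc estimate is shown. The correction is still worth making before the table is programmed, because the fault is definite and cheap to remove.

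**What to change.** Split the rule in SAP 5.4.1.1. Keep the present start-date test for adverse events only. For therapies, add a sentence to this effect: a therapy with a missing or partial start date is concomitant if it is ongoing or ended on or after the date of first dose, unless the known part of its start date is later than last dose plus 30 days. This agrees with the use criterion in 5.7.1 and gives partly dated, fully dated and undated records of the same ongoing drug the same result.

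The cost is one SAP sentence and about one line of code. No new data are needed, because the present algorithm already relies on the end date or ongoing status.
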